6.14.1. Analysis of Adverse Events

6.14.1.1. Treatment Emergent Adverse Events

A treatment-emergent adverse event (TEAE) is defined as an event that first occurred or worsened in severity after baseline. The MedDRA Lowest Level Term (LLT) will be used in the

treatment-emergent derivation. The maximum severity for each LLT during the baseline period including ongoing medical history will be used as baseline severity. For events with a missing severity during the baseline period, it will be treated as “mild” in severity for determining treatment-emergence. Events with a missing severity during the postbaseline period will be treated as “severe” and treatment-emergence will be determined by comparing to baseline severity.

For events occurring on the day of first taking study medication, the case report form (CRF)-collected information (for example, treatment emergent flag, start time of study treatment and event) will be used to determine whether the event was pre- versus post-treatment if available. If the relevant information is not available, then the events will be counted as post-treatment.

The counts and percentages of participants with TEAEs will be summarized by treatment using MedDRA PT nested within SOC. Statistical comparisons will be applied at both the SOC and PT levels. Events will be ordered by decreasing frequency within SOC. The SOC will be in alphabetical order. For events that are sex-specific, the denominator and computation of the percentage will include only participants from the given sex.

An overview of the number and percentage of participants who experienced a TEAE, serious adverse event (SAE), death, discontinued from study treatment or study due to an AE, relationship to study drug will be summarized by treatment.

The counts and percentages of participants with TEAEs by maximum severity will be summarized by treatment using MedDRA PT. For each participant and TEAE, the maximum severity for the MedDRA PT is the maximum postbaseline severity observed from all associated LLTs mapping to the MedDRA PT. The maximum severity will be determined based on the nonmissing severities. If all severities are missing for the defined postbaseline period of interest, it will show as missing in the table.

6.14.1.2. Common Adverse Events

The counts and percentages of participants with TEAEs, overall and common (common TEAEs occurred in $\geq 5\%$ of participants before rounding), will be summarized by treatment using MedDRA PT. Events will be ordered by decreasing frequency.

6.14.1.3. Deaths

A listing of all deaths during the study will be provided. The listing will include participant identification including the treatment, site number, date of death, age at the time of enrollment, sex, cause of death as reported by investigator, cause of death as adjudicated by CEC., etc.

6.14.1.4. Other Serious Adverse Events

The counts and percentages of participants who experienced a SAE (including deaths and SAEs temporally associated or preceding deaths) during the postbaseline period will be summarized by treatment using MedDRA PT nested within SOC. Events will be ordered by decreasing frequency within SOC. The SOC will be in alphabetical order.

A listing of all SAEs will be provided. The listing will include treatment, participant identification including the site number, date of event, age at the time of enrollment, sex, MedDRA SOC and PT, Reported term, severity, outcome, relationship to study drug, time from first dose of study drug to the event, AE start date, AE end date, seriousness, and action taken related to study treatment.

6.14.1.5. Other Significant Adverse Events

The counts and percentages of participants who discontinued from study treatment or study due to an AE during the postbaseline period may be summarized by treatment group using MedDRA PT nested within SOC. Events will be ordered by decreasing frequency within SOC.

6.14.2. Patient Narratives

Patient narratives will be provided for all participants who experience any of the following “notable” events:

- death
- serious adverse event, or
- permanent discontinuation of study treatment due to AEs.

Patient narratives (patient level data and summary paragraph) will be provided for participants in the randomized population with at least 1 notable event.

6.14.3. Special Safety Topics

For adverse events of special interest (AESI) or special safety topics, the counts and percentages of participants will be summarized by treatment and PT with decreasing frequency. Individual participant level data may be presented. Displays with individual participant level data may be created using various formats, such as a customized listing and/or a customized graphical participant profile. Adverse events of special interest are defined in each section of special safety topics, where applicable.

6.14.3.1. Acute Gallbladder Disease

All events of TEAE biliary colic, cholecystitis, or other suspected events related to gallbladder disease will be summarized by treatment groups by PT with decreasing frequency. Detailed searching criteria can be found in [Appendix 3](#).

6.14.3.2. Amputation/Peripheral Revascularization

This section is applicable for participants developing T2DM during the study treatment (up to primary database lock [72 weeks] and final database lock [176 weeks]).

Treatment-emergent amputation/peripheral revascularization will be considered as AESIs. The counts and percentages of participants with amputations/peripheral revascularization may be summarized by treatment.

6.14.3.3. Exocrine Pancreas Safety

6.14.3.3.1. Pancreatic Enzyme

Observed pancreatic enzyme data (p-amylase and lipase) will be summarized by treatment and nominal visit.

The counts and percentages of participants with maximum postbaseline pancreatic enzyme value exceeding the following thresholds will be provided by baseline pancreatic enzyme value (\leq upper limit of normal [ULN], $>$ ULN), and postbaseline: ≤ 1 x ULN, (>1 to ≤ 3) x ULN, (>3 to ≤ 5) x ULN, (>5 to ≤ 10) x ULN, >10 x ULN.

An MMRM analysis will be used to analyze each pancreatic enzyme with a log transformed (postbaseline measure/baseline measure) response variable and treatment, nominal visit, treatment-by-nominal visit interaction as fixed effects.

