6.3. Measures to Minimize Bias: Randomization and Blinding

This is a double-blind study.

Participants who meet all criteria for enrollment will be randomized to one of the study treatment groups at Visit 3. Assignment to treatment groups will be determined by a computer-generated, random sequence using an IWRS. Participants will be randomized in a 1:1:1:1 ratio to receive tirzepatide 5 mg, tirzepatide 10 mg, tirzepatide 15 mg, or placebo.

The randomization will be stratified by prediabetes status, country, and sex (female, male).

Investigators, site staff, clinical monitors and participants will remain blinded to the treatment assignments until the study is complete. To preserve the blinding of the study, a limited number of individuals from the Sponsor will be unblinded to treatment assignments as needed for the interim analysis and for the primary endpoint (Week 72) database lock (see Section 9.5).

Emergency unblinding may be performed through the IWRS. This option may be used ONLY if the participant's wellbeing requires knowledge of the participant's treatment assignment. All emergency unblinding events are recorded and reported by the IWRS.

If an investigator, site personnel performing assessments, or participant is unblinded, the participant must be discontinued from the study. In cases where there are ethical reasons to have the participant remain in the study, the investigator must obtain specific approval from a Lilly clinical research physician (CRP) for the participant to continue in the study.

In case of an emergency, the investigator has the sole responsibility for determining if unblinding of a participant's treatment assignment is warranted for medical management of the event. The participant safety must always be the first consideration in making such a determination. If a participant's treatment assignment is unblinded, Lilly must be notified immediately. If the investigator decides that unblinding is warranted, it is the responsibility of the investigator to promptly document the decision and rationale and notify Lilly as soon as possible.

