6.3. Adjustments for Covariates

The study is stratified by prediabetes status at randomization, country, and sex (female, male). Where necessary to be included as a stratification factor, countries with fewer than 10 randomized participants will be pooled into 1 category (pooled country).

Unless otherwise specified, for efficacy related analyses at 72 weeks, country/pooled country, sex, prediabetes status at randomization and corresponding baseline value will be used as a covariate. For efficacy analyses at 176 weeks (or 193 weeks), country/pooled country, sex and corresponding baseline value will be used as a covariate.

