6.14. Safety Analyses

Unless specified otherwise, safety assessments will be based on the SS (Table GPHK.6.1). All events that occur between the first dose date of study drug and the end date of study participation will be included, regardless of the adherence to study drug.

The statistical assessment of homogeneity of the distribution of categorical safety responses between tirzepatide doses and placebo will be conducted using Fisher's exact test, unless specified otherwise.

For selected continuous safety parameters, the mean change from baseline differences vs. placebo will be assessed via a MMRM using REML. Data from scheduled visits will be utilized for this analysis. Unless specified otherwise, the model for the analysis during 72 weeks treatment period will include country/pooled country, sex, prediabetes status at randomization, treatment group, visit and treatment-by-visit interaction as fixed effects, and baseline value of the safety parameter as a covariate. For the analysis during the 176 weeks treatment period (or 193 weeks), only participants with prediabetes at randomization in the SS will be included, and the model will contain the terms of country/pooled country, sex, treatment group, visit and treatment-by-visit interaction as fixed effects, and baseline value of the safety parameter as a covariate. To model the covariance structure within participants, the unstructured covariance matrix will be used. If this model fails to converge, the covariance structures specified in Section 6.13.1.1 will be tested in order until met convergence. If the data does not warrant the MMRM model, then ANCOVA model will be conducted.

For selected safety parameters, time-to-first-event analysis via the Cox-proportional hazards model may be conducted. Participants without the event will be censored at the end of study participation. For participants experiencing the event, the "time-to-first-event" will be the time (in days) from first dose to first occurrence of the event.

Where necessary, the rate of events will be analyzed using a generalized linear mixed-effects model assuming the number of events follow a negative binomial distribution and with treatment as a fixed effect. The logarithm of days during the active treatment period will be adjusted as an offset to account for possible unequal treatment duration of follow-up between participants.

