6.14.3.14. Renal Safety

Laboratory measures related to renal safety will be analyzed as specified for laboratory measurements in Section [6.14.6](#).

Two shift tables examining renal function will be created. A min-to-min shift table of estimated glomerular filtration rate (eGFR) estimated by the Chronic Kidney Disease Epidemiology Collaboration (CKD-EPI) equation with units ml/min/1.73m², using categories (<30, ≥30 to <45, ≥45 to <60, ≥60 to <90, and ≥90 mL/min/1.73m²). A max-to-max shift table of urine albumin-to-creatinine ratio (UACR), using the categories UACR <30 mg/g, 30 mg/g ≤ UACR ≤ 300 mg/g, UACR >300 mg/g (respectively, these represent normal, microalbuminuria, and macroalbuminuria).

Mixed model repeated measure analyses for eGFR and UACR will be provided. Log transformation will be performed for UACR.

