6.14.4. Vital Signs

In the case that multiple records of an individual vital sign are collected at the same visit, they will be averaged prior to being used for data summaries and analyses.

Descriptive summaries by treatment and by nominal visit will be provided for baseline and postbaseline values as well as change from baseline values.

An MMRM and/or an ANCOVA model as in Section [6.14](#) might be conducted if necessary.

Counts and percentages of participants with treatment-emergent abnormal sitting SBP, sitting DBP, and pulse at any time during the entire study (including the off-drug follow up time period) will be presented by treatment for participants who have both baseline and at least 1 postbaseline result. A treatment-emergent high result is defined as a change from a value less than or equal to the high limit at baseline to a value greater than the high limit at any time that meets the specified change criteria during the postbaseline period. A treatment-emergent low result is defined as a change from a value greater than or equal to the low limit at baseline to a value less than the low limit at any time that meets the specified change criteria during the postbaseline period. To assess decreases, change from the minimum value during the baseline period to the minimum value during the postbaseline period will be used. To assess increases, changes from the maximum value during the baseline period to the maximum value during the postbaseline period will be used. Both planned and unplanned measurements will be included in the analysis. The criteria for identifying participants with treatment-emergent vital sign abnormalities are stated in [Table GPHK.6.11](#).

Table GPHK.6.11. Categorical Criteria for Abnormal Treatment-Emergent Blood Pressure and Pulse Measurements

Parameter	Low	High
Systolic BP (mm Hg) (Supine or sitting – forearm at heart level)	≤90 and decrease from baseline ≥20	≥140 and increase from baseline ≥20
Diastolic BP (mm Hg) (Supine or sitting – forearm at heart level)	≤50 and decrease from baseline ≥10	≥90 and increase from baseline ≥10
Pulse (bpm) (Supine or sitting)	<50 and decrease from baseline ≥15	>100 and increase from baseline ≥15

Abbreviations: BP = blood pressure; bpm = beats per minute

In addition, following analyses will be conducted by treatment:

- counts and percentages of participants who had resting heart rate changes from baseline at 2 consecutive visits of more than 10 bpm and/or 20 bpm

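### The pancreatic-enzyme MMRM leaves out the SAP's default baseline covariate and strata without a reason, and the DXA, 72-week OGTT and ABPM models carry none of the randomization strata (minor)

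*SAP*

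**What the plan says.** Protocol 6.3 and SAP 6.3 stratify randomization by prediabetes status, country and sex. SAP 6.14 sets a default 72-week safety MMRM with "country/pooled country, sex, prediabetes status at randomization, treatment group, visit and treatment-by-visit interaction as fixed effects, and baseline value of the safety parameter"; the last of these enters as a covariate. It applies unless a later section specifies something else. For the 176-week version, "only participants with prediabetes at randomization in the SS will be included", and prediabetes status drops out of the model. SAP 6.3 has a parallel efficacy default: "for efficacy related analyses at 72 weeks, country/pooled country, sex, prediabetes status at randomization and corresponding baseline value will be used as a covariate".

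Four analyses state shorter models:

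- **Pancreatic enzymes (SAP 6.14.3.3.1):** an MMRM on the log of postbaseline over baseline, with this "response variable and treatment, nominal visit, treatment-by-nominal visit interaction as fixed effects".
- **72-week OGTT (SAP 6.14.6.1):** the four arms and the baseline value.
- **DXA (SAP Appendix 1):** pooled tirzepatide versus placebo, and the baseline value.
- **ABPM (SAP Appendix 2):** the four arms, the baseline value, and baseline use of heart-rate-controlling medicine.

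Other safety measures keep the default. For vital signs the SAP points back with "An MMRM and/or an ANCOVA model as in Section" 6.14. For renal function it says only "Mixed model repeated measure analyses for eGFR and UACR will be provided", with no term list, so the default applies there too.

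**The concern.** A log ratio adjusts for baseline only in one fixed way: it forces the slope of log follow-up on log baseline to be 1. If the true slope differs, a model with log baseline as a covariate is more precise. It is also protected when dropout depends on baseline differently by arm. Without that covariate, losing high-baseline participants from one arm shifts the mean change in those who remain.

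Stratified randomization removes between-arm variation due to the strata. A model that ignores the strata still counts that variation as noise, so its standard error is too large and its test conservative. In a safety comparison, a needlessly wide interval can hide a signal.

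No reason is given, so a programmer cannot tell an intended departure from an abbreviated list. Related laboratory measures may then be adjusted differently by accident.

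**Working it through.** The plan states no figure on this point, so there is none to reproduce. The check is a comparison of terms followed by sizing under stated assumptions. The documents give no correlation, SD ratio, partial R², number of countries or DXA sample size; all of these are assumed below.

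**1. Terms present**

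| Model | Baseline covariate | Country | Sex | Prediabetes status |
|---|---|---|---|---|
| SAP 6.14 default, 72 weeks | yes | yes | yes | yes |
| Pancreatic enzymes | not listed | no | no | no |
| OGTT, 72 weeks | yes | no | no | no |
| DXA | yes | no | no | no |
| ABPM | yes | no | no | no |

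**2. Enzyme standard error.** Let ρ be the correlation of log baseline with log follow-up, and k the follow-up SD divided by the baseline SD. The variance ratio, with versus without log baseline, is k²(1−ρ²)/(1+k²−2ρk).

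- k = 1, ρ = 0.5: 0.75/1.00 = 0.75, SE ratio 0.866 (13.4% lower).
- k = 1, ρ = 0.9: 0.19/0.20 = 0.95, SE ratio 0.975 (2.5% lower).
- k = 1.25, ρ = 0.5: 1.1719/1.3125 = 0.893, SE ratio 0.945.
- k = 1.25, ρ = 0.8: 0.5625/0.5625 = 1, no gain, because the slope ρk is then exactly 1.

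A complete-data simulation with 600 per arm and k = 1 gave without/with variance ratios of 1.32 and 1.18 at ρ = 0.5 and 0.7 (formula 2/(1+ρ): 1.33 and 1.18). Neither model was biased.

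**3. Enzyme bias under dropout.** Enzymes are measured at Weeks 12, 24 and 72 (Protocol 1.3.1). The simulation used 600 per arm, a true difference of 0, a common correlation ρ, an unstructured covariance and 3000 trials. Cumulative missingness was 10%, 15% and 25%; the 25% is the dropout rate in Protocol 9.2 and the earlier split is assumed. Dropout log-odds rise by 0, 0.5 or 1.0 per baseline SD on tirzepatide and by 0 on placebo.

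| ρ | Bias at Week 72 without baseline, SD (slope 0 / 0.5 / 1.0) | Type I error (same order) |
|---|---|---|
| 0.5 | 0.000 / 0.039 / 0.072 | 0.051 / 0.093 / 0.201 |
| 0.7 | 0.001 / 0.023 / 0.041 | 0.048 / 0.072 / 0.130 |
| 0.9 | 0.000 / 0.008 / 0.013 | 0.049 / 0.059 / 0.076 |

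With baseline in the model the absolute bias was at most 0.002 SD.

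**4. Omitted strata.** If the strata explain a share R² of the remaining variance and balance is complete, the reported SE is too large by 1/√(1−R²) and the actual alpha is 2[1−Φ(1.96/√(1−R²))]. At R² = 0.02, 0.05 and 0.10 the factors are 1.010, 1.026 and 1.054, and alpha is 0.0477, 0.0443 and 0.0388.

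Missing data weaken the balance, so the OGTT case was simulated with 5000 trials. It used 2400 participants in blocks of 4 within 9 countries (both assumed), 30% men (the complement of the 70% cap on women), 60% prediabetes (Protocol 9.2) and 25% missing at random. Sex and prediabetes status were then added to the model:

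| Partial R² | Change in reported SE | Change in true SE |
|---|---|---|
| 0 | +0.01% | +0.04% |
| 0.02 | −0.99% | −0.34% |
| 0.05 | −2.53% | −0.91% |
| 0.10 | −5.13% | −1.27% |

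At R² = 0.10, type I error moved from 0.041 to 0.050 (Monte Carlo error about 0.003).

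For ABPM at R² = 0.10 the true gain depends on how the sub-study is recruited. With all participants of two countries (about 533), the reported SE falls 5.1% and the true SE 0.1%, and type I error moves from 0.038 to 0.049. With a random 576 of 2400, the falls are 5.0% and 4.7%, because trial-wide stratification then balances the sub-study only partly.

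**5. Degrees-of-freedom cost.** The reported-SE factor is √[(1−R²)(N−p)/(N−p−q)], with p terms already present and q added. For sex and prediabetes status, q = 2.

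- ABPM, N about 576 (Protocol 9.5), p = 6: √(570/568) = 1.0018, or +0.18% at R² = 0; −4.96% at R² = 0.10. Break-even R² = 1 − 568/570 = 0.35%.
- OGTT, p = 5: +0.04% (N = 2400) and +0.06% (N = 1800) at R² = 0.
- DXA, p = 3, assumed N = 100: √(97/95), or +1.05% at R² = 0 and −4.14% at R² = 0.10. Assumed N = 300: +0.34% and −4.81%.

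Adding country as well, with an assumed 5 to 15 levels, gives these costs at R² = 0: ABPM 0.53% to 1.43%; OGTT 0.13% to 0.45% across both N; DXA 1.03% to 2.81% at N = 300 and 3.24% to 9.43% at N = 100.

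**The case against.** **The departure is allowed.** The default yields to any later section that specifies a model, and the SAP never promises a reason. This stands: there is no contradiction, only an unexplained choice.

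**Baseline may still be inherited.** The enzyme sentence lists fixed effects, whereas the default names baseline separately as a covariate, so one could read baseline as still included. This is possible, and on that reading steps 2 and 3 fall away. It does not rescue the strata, which are fixed effects in the default and absent from the list. SAP 6.14.6 also allows an MMRM for selected laboratory tests without naming terms, but does not say that the enzymes are among them.

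**The bias scenario has no support in the documents.** Protocol 7.1 lists diagnosed pancreatitis, not enzyme level, as a reason to stop drug. Participants who stop are asked to keep attending, and the safety set keeps off-drug data. This stands. The bias figures, including the type I error of 0.201, are conditional illustrations; without dropout that depends on arm and baseline together, the bias is nil.

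**The sub-studies may have their own reasons.** The DXA and ABPM addenda are not in the file, and sparse countries would be a fair reason to leave country out. This stands for country. It does not explain leaving out sex and prediabetes status, which use two degrees of freedom.

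**A separate OGTT gap.** SAP 6.14.6.1 applies its model to parameters that it says follow, but no list follows. That needs its own clarification.

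**Conclusion.** The concern holds as a minor point. The enzyme model lists neither the default baseline covariate nor any stratum, and the DXA, 72-week OGTT and ABPM models omit all three strata, with no reason stated in the protocol or SAP.

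The main consequence is lost precision and slightly conservative tests. The enzyme SE gain ranges from nil to 13.4% over the correlations (0.5 to 0.9) and SD ratios examined. For the OGTT model the true SE gain is at most about 1.3% up to a partial R² of 0.10. Bias in the enzyme comparison is possible only under joint dependence of dropout on arm and baseline.

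The practical stakes are further limited. None of these analyses is in the type 1 error strategy. Enzymes are also tabulated by multiples of the upper limit of normal, split by baseline, and OGTT parameters are also summarized by glycemic status.

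**What to change.** - **SAP 6.14.3.3.1:** add log baseline enzyme, country/pooled country and sex, plus prediabetes status in the 72-week analysis of all participants. Alternatively, say in one sentence that the 6.14 default covariates apply. If the shorter model is intended, state why.
- **SAP 6.14.6.1 (72-week OGTT):** add sex, prediabetes status at randomization and pooled country.
- **SAP Appendices 1 and 2 (DXA, ABPM):** add sex and prediabetes status. Add pooled country only where numbers allow. The rule in SAP 6.3 that pools countries below 10 participants counts the whole trial, so re-apply it to sub-study counts.
- **176-week analyses restricted to prediabetes:** leave prediabetes status out, because it is constant there.

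This changes model statements only and needs no new data. If sex and prediabetes status turn out to have no prognostic value, the cost is the R² = 0 figures in step 5. Including country can become expensive only in a small DXA sub-study, which is why it is conditional there.
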